### 8.3.2. Pregnancy

#### Collection of pregnancy information

*Male participants with partners who become pregnant*

- The investigator will attempt to collect pregnancy information on any male participant's female partner who becomes pregnant while the male participant is in this study. This applies only to male participants who receive study intervention.
- After obtaining the necessary signed informed consent from the pregnant female partner directly, the investigator will record pregnancy information on the appropriate form and submit it to the sponsor within 24 hours of learning of the partner's pregnancy. The female partner will also be followed to determine the outcome of the pregnancy. Information on the status of the mother and child will be forwarded to the sponsor. Generally, the follow-up will be no longer than 6 to 8 weeks following the estimated delivery date. Any termination of the pregnancy will be reported regardless of gestational age, fetal status (presence or absence of anomalies) or indication for the procedure.

*Female participants who become pregnant*

- The investigator will collect pregnancy information on any female participant who becomes pregnant while participating in this study. The initial information will be recorded on the appropriate form and submitted to the sponsor within 24 hours of learning of a participant's pregnancy.
- The participant will be followed to determine the outcome of the pregnancy. The investigator will collect follow-up information on the participant and the neonate and the information will be forwarded to the sponsor. Generally, follow-up will not be required for longer than 6 to 8 weeks beyond the estimated delivery date. Any termination of pregnancy will be reported, regardless of gestational age, fetal status (presence or absence of anomalies) or indication for the procedure.
- While pregnancy itself is not considered to be an AE or SAE, any pregnancy complication or elective termination of a pregnancy for medical reasons will be reported as an AE or SAE.
- A spontaneous abortion (occurring at <20 weeks gestational age) or still birth (occurring at  $\geq 20$  weeks gestational age) is always considered to be an SAE and will be reported as such.
- Any post-study pregnancy-related SAE considered reasonably related to the study intervention by the investigator will be reported to the sponsor as described in protocol Section 8.3.1. While the investigator is not obligated to actively seek this information in former study participants, he or she may learn of an SAE through spontaneous reporting.
- Any female participant who becomes pregnant while participating in the study will discontinue study intervention. If the participant is discontinued from the study, follow the standard discontinuation process. The follow up on the pregnancy outcome should continue independent of intervention or study discontinuation.

**8.4. Pharmacokinetics**

PK parameters are not evaluated in this study.

**8.5. Pharmacodynamics**

PD parameters are not evaluated in this study.

**8.6. Genetics**

Genetics is not evaluated in this study.

**8.7. Biomarkers**

Biomarkers are not evaluated in this study.

**8.8. Immunogenicity Assessments**

Immunogenicity assessments are not evaluated in this study.

**8.9. Health Economics**

Medical resource utilization and health economics parameters are not evaluated in this study.

## 9. Statistical Considerations

The SAP will be finalized prior to unblinding, and it will include a more technical and detailed description of the statistical analyses described in this section. This section is a summary of the planned statistical analyses of the most important endpoints, including primary and key secondary endpoints.

### 9.1. Statistical Hypotheses

The primary objective is to demonstrate that galcanezumab is superior to rimegepant in reducing migraine headaches as measured by average monthly response rate across a 3-month period (in this case, the 3-month double-blind period). If one lets  $\pi_G$  and  $\pi_R$  = the true 3-month average monthly 50% response rates for galcanezumab and rimegepant respectively, *the null and alternative hypotheses are as follows:*

$$H_0: \pi_G \leq \pi_R \text{ against } H_a: \pi_G > \pi_R$$

The corresponding hypotheses for secondary objectives with response rate based estimands (for example, average monthly 75% response rate) are identical as those for the primary (with corresponding changes to the true response rate of interest).

For secondary objectives that are to demonstrate the superiority of galcanezumab over rimegepant as measured by continuous measures (for example, reduction from baseline in monthly migraine headache days), the null and alternative hypotheses would be of the form:

$$H_0: \mu_G \leq \mu_R \text{ against } H_a: \mu_G > \mu_R$$

Where  $\mu_G$  and  $\mu_R$  are the true mean reductions for galcanezumab and rimegepant, respectively.

While all hypotheses given above are 1-sided, these hypotheses will operationally be evaluated via 2-sided tests.

#### 9.1.1. Multiplicity Adjustment

The statistical comparisons for the primary efficacy endpoint and the key secondary endpoints will be carried out in the hierarchical order as indicated in Section 3. This means that statistically significant results for the comparison in the higher rank (primary, then ranked secondary variables) are required to initiate the testing of the next comparison in the lower rank. Since a step-down procedure is used, each comparison will be tested at a significance level of 0.05 and an overall alpha level of 0.05 will be preserved.

The order of objectives/comparisons may change (with the exception of the primary objective). Should such a change take place, the final hierarchical order used/multiplicity adjustment approach employed to ensure overall 0.05 alpha-level control will be documented within an approved final SAP prior to study unblinding.

## 9.2. Analyses Sets

Participant Analysis Set	Description
Intention to Treat (ITT) set	All randomized participants and receive at least 1 dose of study intervention. Participants will be included in the analyses according to their randomized treatment.
Safety analysis set	All participants who are exposed to study intervention. Participants will be analyzed according to the treatment they actually received.

## 9.3. Statistical Analyses

### 9.3.1. General Considerations

Statistical analysis of this study will be the responsibility of Lilly or its designee. Details of statistical analysis methods will be described in the SAP with the final SAP approved prior to study unblinding being the official version for this study.

Unless otherwise specified, analyses will be conducted on the ITT population for efficacy analyses and on the safety population for safety analyses (see Section 9.2). When change from baseline is assessed, the participant will be included in the analysis only if he/she has a baseline and a postbaseline measurement.

Binary efficacy variables with repeated measures will be analyzed using a GLIMMIX as pseudo-likelihood-based mixed effects repeated measures analysis. The GLIMMIX model will include the fixed, categorical effects of treatment, month, and treatment-by-month interaction, as well as the continuous, fixed covariate of baseline monthly migraine headache days value.

For binary efficacy variables without repeated measures, comparisons between treatment groups will be performed using logistic regressions with LOCF imputation being used. This model will include the main effects of treatment and a continuous effect for baseline monthly migraine headache days.

Continuous efficacy variables with repeated measures will be analyzed using MMRM methods. The MMRM will include the fixed categorical effects of treatment, month, and treatment-by-month interaction, as well as the continuous fixed covariates of baseline and baseline-by-month interaction. Wherever possible an unstructured covariance matrix will be used to model the correlation structure among repeated measures. A list of other covariance structures to be used in case of nonconvergence will be given within the SAP.

For continuous efficacy variables without repeated measures, an ANCOVA model with LOCF imputation will be used, which contains the main effects of treatment, and the continuous fixed covariate of baseline. Type III sum-of-squares for the LSMeans will be used for the statistical comparisons.

For continuous safety variables with repeated measures, MMRM methods will be used, as well as an ANCOVA model with LOCF imputation if deemed appropriate. When an ANCOVA

model is used for safety measures, the model will contain the main effect of treatment, as well as the continuous fixed covariate of baseline. Type III sum-of-squares for the LSMeans will be used for the statistical comparisons.

For categorical safety variables (such as AEs and other categorical changes of interest), comparisons between treatment groups will be performed using Fisher's exact test.

Treatment effects will be evaluated based on a 2-sided significance level of 0.05 for all the efficacy and safety analyses unless otherwise stated. The 95% confidence intervals for the difference in LSMeans between treatment groups will be presented. Type I error due to multiple comparisons for the primary and key secondary objectives will be controlled using sequential gating procedure (see Section 9.1.1). There will be no adjustments for multiplicity for analyses of other data (other secondary objectives or tertiary objectives).

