### 1.3. Schedule of Activities (SoA)

SP I – Screening		SP II – Prospective Baseline	SP III – Double-Blind Treatment				ET	Comments
Visit 1 procedures may be conducted over more than 1 day as long as all activities are completed within the allowable visit tolerance.								
Visit Number	1	2	3	4 a	5 a	6		
Month relative to randomization (V3)	*	**		1	2	3		
*Screening lasts from 3 to 30 days.
 
** Eligibility is determined between a minimum of 30 days and a maximum of 40 days. Investigators have up to 5 additional days, if needed, to schedule participant's Visit 3 appointment.
 
For scheduling purposes, a month is 30 days.

Interval allowance (days)			-	±2	±2	±2		
Telephone Visit				X	X			See footnote a.
Informed consent	X							The ICF must be signed before any protocol-specific tests or procedures are performed.
Inclusion and exclusion, review and confirm	X	X	X					
Demographics	X							
Medical history	X							
Substance use	X							Substances: alcohol, caffeine, nicotine, tobacco
Concomitant medications	X	X	X	X	X	X		
AE	X	X	X	X	X	X		Any events that occur after signing the ICF are considered AEs as defined in Section 10.3.
Physical Evaluation								
Height	X							
Weight	X							
12-lead ECG (local)	X					X	X	
ECGs should be collected prior to blood draws. Participants should be supine for approximately 5 to 10 minutes before ECG collections and remain supine but awake during the ECG collection.
 
See Section 8.2.3 for additional details.

Vital signs	X		X			X	X	Includes body temperature, sitting blood pressure, and pulse.

SP I – Screening		SP II – Prospective Baseline	SP III – Double-Blind Treatment				ET	Comments
Visit 1 procedures may be conducted over more than 1 day as long as all activities are completed within the allowable visit tolerance.			1	2	3	4 a	5 a	6
Visit Number	1	2						
Month relative to randomization (V3)	*	**		1	2	3		
*Screening lasts from 3 to 30 days.
 
** Eligibility is determined between a minimum of 30 days and a maximum of 40 days. Investigators have up to 5 additional days, if needed, to schedule participant's Visit 3 appointment.
 
For scheduling purposes, a month is 30 days.

Interval allowance (days)			-	±2	±2	±2		
Telephone Visit				X	X			See footnote a.
								Blood pressure and pulse will be measured in triplicate after participant has been sitting for at least 5 minutes, and prior to blood draws.
Physical examination	X							

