##### **9.3.4.2. Vital Signs**

Vital signs collected during the study include systolic and diastolic blood pressure, pulse, and temperature. For vital signs procedures see Section [8.2.2](#).

The number and percentage of participants meeting criteria for treatment-emergent abnormalities in vital signs at any time during study will be summarized. Treatment group comparisons will be performed using Fisher's exact test.

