3.3. CHANGES TO ANALYSIS FROM PROTOCOL

In addition to the exploratory objectives and endpoints specified in the protocol, this SAP contains additional exploratory objectives and endpoints to assess onset of action, sustained response, and other endpoints of interest. See Section 2.3 for details.

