5.2. SAFETY ANALYSIS SET (SAF)

The safety analysis set (SAF) will contain all participants who are exposed to study intervention (either injection or ODT). Participants will be analyzed according to the treatment they actually received.

If there is any doubt whether a participant was treated or not, it will be assumed that the

Document: CCI

Author: PPD

Version Number:

3.0

Version Date:

19May2023

CCI

participant has been treated for the purposes of analysis.

When change from baseline is assessed, the participant will be included in the analysis only if the participant has a baseline and a postbaseline measurement.

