20. SAFETY OUTCOMES

Safety endpoints consist of incidences of treatment emergent adverse events (TEAEs), serious adverse events (SAEs) and adverse events (AEs) in general and leading to discontinuation, vital signs (blood pressure, pulse, and body temperature), weight and laboratory measures (chemistry, hematology, and urinalysis). All outputs for safety outcomes will be based on the Safety Analysis Set.

For categorical safety variables (such as AEs and other categorical changes of interest), comparisons between treatment groups will be performed using Fisher's exact test.

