20.3. VITAL SIGNS

Vital signs include body temperature, blood pressure, and pulse. Blood pressure and pulse will be measured in triplicate in the sitting position after the participant has rested for at least 5

Document: CCI

Author: PPD

Version Number:

3.0

Version Date:

19May2023

CCI

minutes, and before collection of blood samples and dosing (if dosing is on the same day), according to the SoA, and following the study-specific recommendations included in the Reference Manual for the study.

The baseline criteria for determining treatment-emergent vital sign abnormalities are:

- Participants will be defined as having a treatment-emergent low value if they have all normal or high values at all predose/baseline visits, followed by a value below the lower reference limit at any post-baseline visit. Participants with all normal or high values at all predose/baseline visits (no low values) will be included in the analysis of treatment-emergent low values.
- Participants will be defined as having a treatment-emergent high value if they have all normal or low values at all predose/baseline visits, followed by a value above the upper reference limit at any post-baseline visit. Participants with all normal or low values at baseline (no high values) will be included in the analysis of treatment-emergent high values.

The number and percent of participants meeting criteria for treatment-emergent abnormalities in vital signs at any time during study will be summarized. Treatment group comparisons will be performed using Fisher's exact test.

Table L displays the criteria used to define treatment emergent changes in vital signs and weight. The last column of the table displays the participant populations defined by baseline categories, the treatment-emergent categorical changes will be analyzed for each of those participant populations. The criteria generally consist of 2 parts, an absolute threshold and a change from baseline amount. The baseline and post-baseline definitions for vital signs analyses are in Table F

Table L displays the criteria for categorical changes of interest in vital signs. The last column of the table displays the participant populations defined by baseline categories. All vital signs data will be listed.

Document: CCI

Author: PPD

Version Number:

3.0

Version Date:

19May2023

CCI

Table L: Criteria for Categorical Changes of Interest in Vital Signs

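### The protocol's general provision for modelling continuous safety variables goes unused without a record, leaving blood pressure compared between arms only by a threshold rule that is insensitive to small mean shifts

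*Protocol*

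**What the plan says.** Protocol 9.3.1 sets a general rule: "For continuous safety variables with repeated measures, MMRM methods will be used, as well as an ANCOVA model with LOCF imputation if deemed appropriate". It fixes the ANCOVA terms as treatment and baseline, and it calls for 95% confidence intervals on differences in LS means.

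The protocol's specific safety sections are narrower. Section 9.3.4.2 says: "The number and percentage of participants meeting criteria for treatment-emergent abnormalities in vital signs at any time during study will be summarized", with Fisher's exact test for the comparison. Section 9.3.4.3 treats laboratory tests the same way.

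The SAP follows the specific sections. Section 20 states: "For categorical safety variables (such as AEs and other categorical changes of interest), comparisons between treatment groups will be performed using Fisher's exact test". It has no counterpart for continuous safety variables. Section 20.3 says: "The number and percent of participants meeting criteria for treatment-emergent abnormalities in vital signs at any time during study will be summarized". Table L sets the criteria: the high-direction rule for systolic pressure is at least 140 mm Hg with a rise of at least 20, and for diastolic at least 90 with a rise of at least 10. Table F takes the maximum over Visits 1 to 3 as baseline for the high direction, and it has no row for continuous safety change.

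SAP 3.3 lists one kind of departure from the protocol: "this SAP contains additional exploratory objectives and endpoints to assess onset of action, sustained response, and other endpoints of interest". Safety is not mentioned.

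Some SAP text does assume quantitative safety data. Section 5.2 keeps a rule for the safety set: "When change from baseline is assessed, the participant will be included in the analysis only if the participant has a baseline and a postbaseline measurement". Section 6.2 averages triplicate pulse and blood pressure into visit values. Section 20.2.1 converts laboratory values beyond the quantification limits for use in quantitative summaries.

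**The concern.** Vital signs and laboratory measures are named secondary safety endpoints, and blood pressure is measured in triplicate at Visits 1, 3 and 6 or early termination. If the only comparison between arms is whether a participant crossed a high threshold and also rose by a set amount, most of that information is lost. Few participants in this population would meet both conditions, so a modest difference in mean blood pressure between the two drugs could go unseen. The reader of the report would have a non-significant count comparison and no estimate or interval for the mean difference.

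There is also a documentation gap. The protocol carries a provision that no later section uses, and the place where such a change would be recorded does not mention it.

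**Working it through.** **What was planned and what was carried through.** Four places have to be compared.

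- Protocol 9.3.1: MMRM for continuous safety variables if measures are repeated; ANCOVA with LOCF at discretion.
- Protocol 1.3: vital signs at Visits 1, 3 and 6 or early termination; chemistry, hematology and urinalysis at Visits 1 and 6 or early termination. That is one scheduled post-baseline value per participant, so the condition for MMRM is not clearly met and ANCOVA is the model that fits.
- Protocol 9.3.4.2 and 9.3.4.3: categorical only.
- SAP 20, 20.2, 20.3 and Table F: categorical comparisons only, with no model for a continuous safety variable. SAP 3.3 is silent.

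**Size.** The plan states no power, SD or event rate for blood pressure, so there is no figure to reproduce. The power of more than 85% in Protocol 9.5 concerns the primary endpoint.

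Inputs from the documents: about 575 randomized 1:1 with up to 10% dropout, so 575 × 0.9 / 2 ≈ 259 per arm; two-sided 0.05; the Table L high criteria.

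Assumptions, not in the documents: systolic mean 120, SD 12 to 14; diastolic mean 77, SD 8.5; correlation *r* between baseline and Visit 6 of 0.5 to 0.7; true shifts of 2, 3 and 5 mm Hg.

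Formulas:

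- Crossing probability: among participants with baseline *b* at or below the limit, average 1 − Φ{[max(limit, *b* + rise) − μ − *r*(*b* − μ) − shift] / [SD√(1 − *r*²)]} over the baseline distribution. Power is then that of the exact two-sided Fisher test.
- ANCOVA: residual SD = SD√(1 − *r*²); SE = residual SD × √(2/259); power ≈ Φ(shift/SE − 1.96).

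One case worked through (systolic, SD 12, *r* = 0.5, shift 3 mm Hg):

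- Crossing rates are 1.20% and 2.39%, or about 259 × 0.0120 = 3.1 and 259 × 0.0239 = 6.2 participants. Fisher power is 9.4%.
- Residual SD = 12 × √0.75 = 10.4; SE = 10.4 × √(2/259) = 0.914; 3/0.914 = 3.28; power = Φ(1.32) ≈ 91%.

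This uses one baseline value. Table F's maximum over the baseline visits is stricter, so the calculation was repeated with the maximum of Visits 1 and 3, restricted to eligible participants. The assumptions were similar (for example systolic mean 120 to 122, between-person SD 10 to 12, within-person SD 8).

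| Shift | Fisher, single baseline | Fisher, maximum baseline | ANCOVA |
|---|---|---|---|
| Systolic 2 mm Hg | 0.5–6.5% | 0.3–3% | 44–76% |
| Systolic 3 mm Hg | 2–13% | 1–7% | 77–98% |
| Systolic 5 mm Hg | 14–41% | 7–21% | >99% |
| Diastolic 2 mm Hg | 13–18% | 6–10% | 86% or more |
| Diastolic 3 mm Hg | 36–43% | 15–26% | >99% |
| Diastolic 5 mm Hg | 93% | 72–80% | >99% |

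The ends of these ranges are approximate, not bounds. With correlation 0.7, the maximum-baseline rule can fall below them (for systolic, at SD 12). Fisher power below 5% reflects how conservative the test is with a handful of events.

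The shift detectable with 80% power by a comparison of means is (1.96 + 0.84) × SD × √(2/259): 2.0 mm Hg at SD 8 and 3.4 mm Hg at SD 14.

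The calculation counts Visit 6 only. Table F also admits unscheduled visits, which would add some crossings.

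**The case against.** The strongest reply is that nothing specific was dropped. The protocol's MMRM sentence applies to repeated measures, and only one post-baseline visit is scheduled. ANCOVA was discretionary. The protocol's own vital-sign and laboratory sections are categorical, and the SAP matches them. This stands: a reader might infer that the SAP removed a planned blood-pressure analysis, but the documents show only a general, conditional provision left unused.

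A second reply is that the averaged values may be used beyond thresholds. SAP 5.2, 6.2, 6.3 and 20.2.1 point towards quantitative summaries, and SAP 8 places table content in templates that are not part of the documents. This also stands in part. Descriptive mean-change tables cannot be ruled out, so it is not established that the averages serve only to classify participants. The SAP text still specifies no model or interval for a between-group difference.

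A third reply is that the safety objective is descriptive, so power is not a design criterion. A non-significant Fisher test is also not a finding of no difference, all vital signs are listed, and serious hypertension events are adjudicated. That limits the harm. It does not answer why a more informative estimate from data already collected should be left out, since description is what a mean difference with an interval provides.

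Finally, a reader might infer that the threshold analysis has almost no power for any blood-pressure change. That fits systolic shifts of 2 to 3 mm Hg. It does not fit a diastolic shift of 5 mm Hg, where power is roughly 72 to 93%.

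**Conclusion.** The point holds as a gap between general provision and specified analysis, plus a cheap gain in sensitivity. Protocol 9.3.1 allows for modelling continuous safety variables; no safety section of either document does so, and SAP 3.3 does not say that it was set aside. The threshold comparison is weak for small shifts: roughly 0.3 to 13% power for systolic shifts of 2 to 3 mm Hg and 6 to 43% for the same diastolic shifts, where ANCOVA would have about 44 to 98% and 86% or more. At 5 mm Hg the loss remains clear for systolic (7 to 41% against over 99%) but is modest for diastolic.

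The sizes rest on assumed means, SDs and correlations. The direction held in every combination tried. The documents do not support saying that the SAP withdrew a named blood-pressure analysis, or that the trial would report no difference when one exists.

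**What to change.** In SAP 20.3, add an ANCOVA of change from baseline to Visit 6, or to the early termination value where Visit 6 is missing, with treatment and baseline as terms. Cover at least systolic pressure, diastolic pressure and pulse, using the triplicate mean and the SAP 6.2 baseline. Add the same in SAP 20.2 for continuous laboratory analytes. Report LS mean differences with 95% confidence intervals and make no formal significance claims. Keep the Table L analysis, which answers a different question about individual excursions.

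Align Protocol 9.3.1 with 9.3.4.2 and 9.3.4.3 so that the general and specific sections describe the same analyses. If the sponsor prefers not to model these variables, the least that is needed is a sentence in SAP 3.3 saying that the provision is not used and why.

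The cost is one set of tables from data already collected, and some further unadjusted safety comparisons, which is why intervals are preferable to p-values here.
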